9.5.6 Abuse or Diversion of Study Drug

During the study, the investigator will report any concern about abuse or diversion of study drugs.

Adverse events associated with abuse or diversion will be appropriately reported as AEs and monitored per [Section 9.5.4.3.1](#). Abuse is always to be captured as an AE.

9.5.7 Confirmation of Medical Care by Another Physician

The investigator will instruct subjects to inform site personnel when they are planning to receive medical care by another physician. At each visit, the investigator will ask the subject whether he/she has received medical care by another physician since the last visit or is planning to do so in the future. When the subject is going to receive medical care by another physician, the investigator, with the consent of the subject, will inform the other physician that the subject is participating in the clinical study.

9.6 Data Quality Assurance

This study will be organized, performed, and reported in compliance with the protocol, SOPs, working practice documents, and applicable regulations and guidelines.

9.6.1 Data Collection

Data required by the protocol will be collected in a validated data management system that is compliant with all regulatory requirements. These data include eCRFs, computer tablets and electronic sleep diaries. As defined by ICH guidelines, the CRF is a printed, optical, or electronic document designed to record all of the protocol-required information to be reported to the sponsor on each study subject.

Data collection on the CRF must follow the instructions described in the CRF Completion Guidelines. The investigator has ultimate responsibility for the collection and reporting of all clinical data entered on the CRF. The investigator or designee as identified on Form FDA 1572 must sign the completed CRF to attest to its accuracy, authenticity, and completeness.

Completed, original CRFs are the sole property of Eisai and should not be made available in any form to third parties without written permission from Eisai, except for authorized representatives of Eisai or appropriate regulatory authorities.

9.6.2 Clinical Data Management

All software applications used in the collection of data will be properly validated following standard computer system validation that is compliant with all regulatory requirements. All data, both CRF and external data (eg, laboratory data), will be entered into a clinical system.

9.7 Statistical Methods

Details of the statistical analyses will be included in a separate SAP. All statistical analyses will be performed by the sponsor or designee after the database is locked and released for unblinding. Statistical analyses will be performed using SAS software or other validated statistical software as required. (revised per Amendments 04 and 05)

9.7.1 Statistical and Analytical Plans

The statistical analyses are described in this section. Further details of the analytical plan will be provided in the SAP which will be finalized before database lock and treatment unblinding.

All statistical tests will be based on the 5% level of significance (2-sided).

9.7.1.1 Study Endpoints

The following endpoints will be analyzed for LEM5 and LEM10 compared to PBO.

9.7.1.1.1 PRIMARY ENDPOINT

The primary endpoint will be the mean change from Study Baseline in sSOL at Month 6.

9.7.1.1.2 SECONDARY ENDPOINTS

The key secondary endpoints will be:

- Mean change from Study Baseline in sSE at Month 6
- Mean change from Study Baseline of sWASO at Month 6

Additional secondary endpoints will be:

- Mean change from Study Baseline of sSOL, of sSE, of sWASO and of sTST, at the beginning of treatment (mean of the 7 nights after the 1st dose in Period 1), at Month 1 and at Month 3
- Mean change from Study Baseline of sTST at Month 6
- Proportion of responders at Month 6 and Month 12, where sleep onset responder is defined as follows: sSOL at Study Baseline is ≥ 30 minutes and mean sSOL at 6 months is ≤ 20 minutes, and sleep maintenance responder is defined as follows: sWASO at Study Baseline is ≥ 60 minutes and mean sWASO at 6 months is ≤ 60 minutes and shows a reduction of > 10 minutes compared to Study Baseline.
- Change from Study Baseline in daytime functioning, assessed as the total score from the 4 items on daytime functioning, on the ISI, at Months 1, 3, and 6
- Change from Study Baseline on the FSS at Months 1, 3, and 6
- Ratings on the morning sleepiness item of the Sleep Diary, for:
 - The mean change from Study Baseline of the 1st 7 mornings after the 1st dose in Period 1 and Period 2

- The mean change from Study Baseline at: Month 1, Month 3, and Month 6
- The mean change from Study Baseline and from Period 2 Baseline (as appropriate) for subjects with 1, 3, 6, 9 and 12 months exposure (revised per Amendment 06)
- The mean change from Screening for the 1st 7 mornings and 2nd 7 mornings of the Follow-up Period
- Rebound insomnia endpoints as assessed from the Sleep Diary during the Follow-up Period (revised per Amendment 02)
 - Change from Screening of sSOL on each of the 1st 3 nights, mean sSOL of the 1st 7 nights, and mean sSOL of the 2nd 7 nights of the Follow-up Period
 - Change from Screening of sWASO on each of the 1st 3 nights, mean sWASO of the 1st 7 nights and mean sWASO of the 2nd 7 nights of the Follow-up Period
 - Proportion of subjects whose sSOL is longer than at Screening for each of the 1st 3 nights, or whose mean sSOL is longer than at Screening for 1st 7 nights or 2nd 7 nights of the Follow-up Period
 - Proportion of subjects whose sWASO is higher than at Screening for each of the 1st 3 nights, or whose mean sWASO is higher than at Study Baseline for the 1st 7 nights or 2nd 7 nights of the Follow-up Period
- Persistence of Effect
 - Mean change from Study Baseline of sSOL, of sSE, of sWASO and of sTST at Months 3, 6, 9, and 12 compared to Month 1
 - Mean change from Period 2 Baseline (Month 6) of sSOL, of sSE, of sWASO and of sTST at Months 9 and 12 compared to Month 7 (the 1st month of treatment in Period 2)
 - Mean change from Study Baseline and Treatment Period 2 Baseline (as appropriate) of sSOL, sSE, sWASO and sTST at 3 and 6 months exposure compared to 1 month of exposure (revised per Amendment 06)

9.7.1.1.3 SAFETY ENDPOINTS

Safety and Tolerability of Lemborexant

- During Period 1, compared to PBO
- For subjects exposed to lemborexant for 3, 6, 9, and 12 months (revised per Amendment 06)

9.7.1.1.4 EXPLORATORY ENDPOINTS

The following endpoints will be explored for LEM5 and LEM10. Except for PK endpoints, comparisons to PBO will be made.

- Change from Study Baseline in the mean value of the item on quality of sleep from the Sleep Diary for:
 - The 1st 7 mornings after the 1st dose in Period 1

- Months 1, 3, and 6
- Change from Study Baseline and Period 2 Baseline (as appropriate) in the mean value of the item on quality of sleep from the Sleep Diary for:
 - Subjects with 1, 3, 6, 9, and 12 months exposure (revised per Amendment 06)
- Change from Study Baseline in:
 - EQ-5D-3L at Months 1, 3, and 6
 - WPAI-GH at Months 3 and 6
- Change from Study Baseline and Period 2 Baseline (as appropriate) in:
 - EQ-5D-3L in subjects with 3, 6, 9, and 12 months exposure (revised per Amendment 06)
 - WPAI-GH in subjects with 3, 6, 9, and 12 months exposure (revised per Amendment 06)
- Number and percentage of subjects with a rating of a positive medication effect on each PGI-Insomnia item (1) at Months 1, 3, and 6 (placebo-controlled Treatment Period 1), and (2) with 3, 6, 9, and 12 months exposure (Treatment Period 1 and Treatment Period 2 combined) (revised per Amendment 06)
- Change from Study Baseline and Period 2 Baseline (as appropriate) of sSOL, sSE, sWASO, sTST with 1, 3, 6, 9, and 12 months exposure, and ISI and FSS with 3, 6, 9, and 12 months exposure. (revised per Amendment 06)
- Mean score on the T-BWSQ of LEM5, and LEM10 compared to PBO at End of Study
- Plasma concentrations of lemborexant and its metabolites M4, M9, and M10
- PK of lemborexant using population modeling
- Relationships between lemborexant PK, efficacy, and/or safety variables using PK/PD modeling

9.7.1.2 Definitions of Analysis Sets

- The Safety Analysis Set is the group of subjects who received at least 1 dose of randomized study drug and had at least 1 postdose safety assessment.
- On-Treatment Safety Analysis Set: On-Treatment Safety Analysis Set is the group of subjects who received at least 1 dose of lemborexant and had at least 1 postdose safety assessment (revised per Amendment 06)
- The Full Analysis Set (FAS) is the group of randomized subjects who received at least 1 dose of randomized study drug and had at least 1 postdose primary efficacy measurement.
- On-Treatment Full Analysis Set (FAS): On-Treatment FAS is the group of subjects who received at least 1 dose of lemborexant and had at least 1 postdose primary efficacy measurement. (revised per Amendment 06)

- The Per Protocol Analysis Set is the group of subjects who sufficiently complied with the protocol. Details of the evaluability criteria will be determined before database lock and treatment unblinding and will be specified in the SAP.
- The 6-Months Completer Analysis Set is the group of subjects in the FAS who had all efficacy assessments up to and including Month 6 (ie, Week 1 and Months 1 to 6 visits) without missing primary or key secondary efficacy assessments at any of these visits. (revised per Amendment 04)
- The PK Analysis Set is the group of subjects who have at least 1 quantifiable lemborexant plasma concentration or its metabolites, with adequately documented dosing history.
- The PK/PD Analysis Set is the group of subjects receiving either lemborexant or PBO who have efficacy or safety data with documented dosing history. In addition, subjects receiving lemborexant should have at least 1 quantifiable lemborexant concentration data point as per the PK Analysis Set.

9.7.1.3 Subject Disposition

The number of subjects screened and the number failing screening (overall and by reason for failure) will be summarized. Screen failure data will be listed. The number of subjects randomized along with the number of subjects in each of the study populations will also be presented.

The number of subjects completing the study will be presented. Subjects who prematurely terminated their participation in the study will be summarized by their primary reason for study termination. Subjects who prematurely discontinued from study treatment will also be presented and summarized by primary reason for premature treatment discontinuation. Other reasons for study treatment and study terminations will also be summarized. These tabulations will be produced for all randomized subjects by treatment group.

9.7.1.4 Demographic and Other Baseline Characteristics

Demographic and other baseline characteristics for the Safety Analysis Set will be summarized for each treatment group using descriptive statistics. Continuous demographic variables include age, height, weight, and BMI; categorical variables include sex, age group (<65 years old; ≥65 years old), BMI group (less than 18.5, 18.5 to less than 25, 25 to 30, above 30), race and ethnicity.

Characteristics of insomnia at Study Baseline will be summarized using sSOL, sSE, sWASO, sTST, ISI, and FSS. The BDI-II and BAI scores will also be summarized at Study Baseline.

The demographic data will be summarized by subgroups of age group, sex, BMI group and race. The above tables will be produced for the FAS if it differs from the Safety Analysis Set.

If sufficient numbers of subjects with a particular medical history (major depression, anxiety disorder, chronic pain, etc.) are enrolled, demographic and other baseline characteristics will be summarized for each medical history group using descriptive statistics.

9.7.1.5 Prior and Concomitant Therapy

All investigator terms for medications recorded in the CRF will be coded to an 11-digit code using the World Health Organization Drug Dictionary (WHO-DDE/HD Mar 2014 or latest version). The number (percentage) of subjects who took prior and concomitant medications will be summarized on the Safety Analysis Set by treatment group, Anatomical Therapeutic Chemical (ATC) class, and WHO-DD preferred term (PT). (revised per Amendment 03)

Separate analyses will be provided for the Run-In Period, Treatment Period 1 and Treatment Period 2. (revised per Amendment 03)

For the Run-In Period, a prior medication is defined as a medication that stopped before the 1st dose of study medication in the Run-In Period. For Treatment Period 1, a prior medication is defined as a medication that stopped before the 1st dose of study medication in Treatment Period 1. For Treatment Period 2, a prior medication is defined as a medication that stopped before the 1st dose of study medication in Treatment Period 2. (revised per Amendment 03)

For the Run-In Period, a concomitant medication is defined as a medication that started on or before the 1st dose of study medication in the Run-In Period and continued during some or all of the Run-In Period. For Treatment Period 1, a concomitant medication is defined as a medication that started on or before the 1st dose of study medication in Treatment Period 1 and continued during some or all of that treatment period. For Treatment Period 2, a concomitant medication is defined as a medication that started on or before the 1st dose of study medication in Treatment Period 2. (revised per Amendment 03)

9.7.1.6 Efficacy Analyses

Where Sleep Diary endpoints are described, the time points refer to the mean of the final 7 nights before the visit unless otherwise stated.

Subjects who discontinue the treatment prematurely will be encouraged to continue to complete the assessments at the protocol defined times (retrieved drop out) until the scheduled time of termination. When available, these data will be used for efficacy analyses. If there are a substantial proportion of early withdrawals, a sensitivity analysis of the primary endpoint will be conducted.

Definitions of Baseline

For the analyses of PBO-controlled endpoints (ie, Day 1 to Month 6), “Study Baseline” is defined as the data captured during the Run-In Period (or during the Baseline Period). For the analyses of data that are not placebo-controlled (ie, Month 7 to Month 12), data from Month 6 visit will be used as the “Period 2 Baseline”. (revised per Amendment 06)

For other endpoints, baseline data are captured during the Run-In and Baseline Period. Details will be specified in the SAP.

12-Month Lemborexant Exposure

Twelve-month (12-month) lemborexant exposure summaries will be summarized by treatment (LEM5, LEM10) and duration of exposure (1 month [30 days] where appropriate, 3 months [90 days], 6 months [180 days], 9 months [270 days] and 12 months [365 days]). Treatment groups are LEM5 and LEM10, and include both (a) LEM Period 1 subjects on the

On-Treatment Full Analysis Set using the change from Study Baseline and (b) LEM Period 2 subjects previously receiving PBO on the On-Treatment Full Analysis Set using the change from Period 2 Baseline. (revised per Amendment 06)

Control of Type 1 Error

A sequential gate-keeping procedure including sSOL (primary endpoint), sSE and sWASO (key secondary endpoints) at Month 6 will control for type 1 error. In order to move from 1 step to the next (steps a to f; below) the outcome must be significant at 0.05 (2-sided).

- a. Change from Study Baseline at Month 6 in sSOL, LEM10 compared to PBO
- b. Change from Study Baseline at Month 6 in sSOL, LEM5 compared to PBO
- c. Change from Study Baseline at Month 6 in sSE, LEM10 compared to PBO
- d. Change from Study Baseline at Month 6 in sSE, LEM5 compared to PBO
- e. Change from Study Baseline at Month 6 in sWASO, LEM10 compared to PBO
- f. Change from Study Baseline at Month 6 in sWASO, LEM5 compared to PBO

This testing procedure controls the overall type I error rate of 0.05 for the primary and key secondary efficacy analyses. (revised per Amendment 03).

9.7.1.6.1 ANALYSIS FOR THE PRIMARY ENDPOINT

Null Hypothesis: For sSOL, no difference exists in the mean change from Study Baseline to Month 6 of treatment with LEM10 and LEM5 as compared with PBO.

Alternative Hypothesis: For sSOL, a difference exists in the mean change from Study Baseline to Month 6 for LEM10 and LEM5 as compared with PBO.

The sSOL change from Study Baseline to Month 6 will be analyzed using the mixed effect model repeated measurement (MMRM) analysis on the FAS. The model will include all data and will be adjusted for the corresponding Study Baseline value, region, age group (<65 years old, ≥65 years old), treatment, time (average of the first 7 nights, Month 1, Month 3, and Month 6) and the interaction of treatment by time. An unstructured covariance matrix will be used, and if the model fails to converge, then an autoregressive matrix will be used. The missing values will be imputed using a pattern mixture model utilizing multiple imputation (MI) assuming the missing values are missing not at random (MNAR) utilizing the complete case missing value pattern (CCMV - subjects who completed all primary efficacy assessments without missing values). (revised per Amendment 04) The missing values for a given visit will be imputed using all available values including the retrieved measurement from the post-discontinuation data. The treatment comparison will be performed using contrasts. The p-value, least square (LS) means and the 95% confidence interval (CI) for the treatment difference will also be provided. Details of pattern mixture model and MI method will be presented in SAP. (revised per Amendment 03)

The following analyses will be considered as sensitivity analyses (revised per Amendment 04):

- Missing imputation assuming MNAR utilizing CCMV-7: The same MMRM method used in the primary analysis will be applied utilizing CCMV-7 (ie, up to 7 monotone missing patterns will be used for missing value imputation). (revised per Amendment 04)
- Tipping point analysis: A range of shifts starting from the primary analysis (CCMV) will be used in the multiple imputation of missing data assuming MNAR to identify the specific shift and treatment effect that will tip the results from statistically significant to non-significant. (revised per Amendment 04)

The following analyses will be considered as supplementary analyses (revised per Amendment 04):

- PP analysis: The same primary efficacy analyses described above will be repeated based on PP analysis set.
 - Completer analysis: The same primary efficacy analyses described above will be repeated based on 6-Months Completer Analysis Set. (revised per Amendment 04).
- MMRM analysis assuming MAR: The same primary endpoint analysis described above will be analyzed using MMRM assuming the missing values are missing at random (MAR). (revised per Amendment 03)

9.7.1.6.2 SECONDARY EFFICACY AND PHARMACODYNAMIC ANALYSES

Key Secondary Efficacy Analyses (revised per Amendment 03)

The change from Study Baseline of key secondary endpoints sSE and sWASO at Month 6 comparing LEM5 and LEM10 to PBO will be analyzed using the same analysis method as the primary endpoint. The missing values will be imputed using a pattern mixture model utilizing MI assuming MNAR. The treatment comparison will be performed using contrasts. The p-value, LS means and the 95% confidence interval (CI) of the treatment differences will also be provided. (revised per Amendment 03)

Other Secondary Efficacy Analyses (revised per Amendment 03)

The other secondary efficacy endpoints (change from Study Baseline of the following for LEM5 and LEM10 compared to PBO; mean sSOL, mean sSE, mean sWASO and mean sTST at 1st 7 nights, Months 1 and 3; and mean sTST at Month 6; ISI total of 4 items of daytime functioning at Months 1, 3, and 6, and FSS score at Months 1, 3, and 6) will be analyzed using MMRM, assuming MAR. The FSS will also be analyzed for responders, including only those subjects who endorsed clinically significant fatigue at Study Baseline. (revised per Amendments 03 and 06)

The proportion of responders, separately for sSOL and sWASO, will be analyzed using the Cochran-Mantel-Haenszel test, adjusted for country and age group, after the 1st 7 nights and for the last 7 nights of treatment at the end of Months 1, 3, 6 and 12, for LEM5 and LEM10 compared to PBO.

Rebound insomnia is defined as worsened sleep relative to Screening after study drug treatment is completed. Sleep Diary data from the Follow-up Period will be compared to Sleep Diary data from the Screening Period to assess whether subjects experience rebound

insomnia. Specifically, a higher value for sSOL or sWASO during the Follow-up Period compared to the mean sSOL or sWASO value during the Screening Period will be considered worsened sleep.

To assess rebound insomnia, both categorical analysis at the subject level and continuous analysis at the group mean level will be performed. For each of the first 3 nights and each of the 2 weeks of the Follow-up Period the proportion of subjects whose corresponding value for sSOL or sWASO exceeds the corresponding Screening Period value by 5 minutes will be summarized by treatment group and compared to placebo. The percentage of ‘rebounders’ between each treatment and placebo group will be analyzed using a Cochran-Mantel-Haenszel test, adjusted for country and age group.

To assess statistical significance using the continuous data at the group mean level, the data will be analyzed using ANCOVA, adjusted for country, age group and treatment. The LS mean of each of the first 3 nights and each week of the Follow-up Period will be compared to the Screening Period between each treatment group and placebo. If the lower bound of the 95% CI of sSOL or sWASO for each of the first 3 nights and the mean of each week of the Follow-Up Period exceeds the upper bound of a 95% CI for the values during the Screening Period in the given treatment group, it will be considered strong evidence for rebound insomnia. If the LS means for sSOL and sWASO for the Follow-up Period are all lower than for the Screening Period, then no rebound insomnia is suggested. Otherwise, the degree to which the parameters worsen, and the time point(s) at which they worsen will be considered to evaluate whether clinically meaningful rebound insomnia is present.

To evaluate morning sleepiness item on the Sleep Diary, the mean change from Study Baseline of the 1st 7 mornings after the 1st dose in Period 1, Month 1, Month 3 and Month 6 will be analyzed using MMRM, assuming MAR. Additionally, morning sleepiness change from both Study Baseline and Period 2 Baseline for the 1st 7 mornings after the 1st dose in Period 2, Month 9, and Month 12, and also the change from Screening of each of the 2 weeks of the Follow-Up Period will be summarized with mean and 95% CI's. (revised per Amendment 03)

Analyses for persistence versus loss of effect will be conducted for sSOL, sSE, sWASO and sTST at Months 3, 6, 9, and 12 compared to Month 1. Loss of effect will be defined as present if the mean change from Study Baseline at Month 3 (or Months 6, 9, 12) is below the lower bound of the 95% CI at Month 1 for sSE or sTST and above the upper bound of the 95% CI at Month 1 for sSOL and sWASO. Analyses for persistence versus loss of effect over Period 2 will be conducted for only the subjects randomized to PBO in Period 1 (those subjects will have been randomized to lemborexant in Period 2). These analyses will compare sSOL, sSE, sWASO and sTST at Months 9 and 12 to these measures at Month 7. Loss of effect will be defined as present if the mean change from Period 2 Baseline at Month 9 (or Month 12) is below the lower bound of the 95% CI at Month 7 for sSE or sTST and above the upper bound of the 95% CI at Month 7 for sSOL and sWASO. Analyses for persistence versus loss of effect over duration of exposure will be conducted for On-Treatment Full Analysis Set subjects. These analyses will compare 1 month duration of exposure on sSOL, sSE, sWASO and sTST at 3 and 6 months duration of exposure, for (a) LEM Period 1 subjects using the change from Study Baseline and (b) LEM Period 2 subjects

previously receiving PBO using the change from Period 2 Baseline, with loss of effect as defined above. (revised per Amendment 06)

No multiplicity adjustment is planned for other secondary endpoints. (revised per Amendment 03)

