3.3.2 Adjustments for Covariates

Baseline assessment, region, and age groups are used as covariates in the primary and secondary analyses.

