3.4.2.4 Other Secondary Efficacy Analyses

For all other secondary endpoints described below, the continuous variable will be summarized by using descriptive statistics by time point and the categorical variable will be summarized as the number and percentage of subjects by time point.

Unless is covered from the same model from the primary and secondary efficacy endpoints, or specified otherwise, the change from baseline assessments will be analyzed using MMRM assuming MAR (no missing value imputation) and the portion of responders will be analyzed using the Cochran Mantel Haenszel (CMH) test adjusted for region and age group. Missing values will be considered as non-responders in all responder analyses. No multiplicity adjustment will be made for all analyses.

The following endpoints will be analyzed.

EFFICACY MEASURES DERIVED FROM THE SLEEP DIARY

- Change from Study Baseline of mean sSOL, mean sSE, mean sWASO and mean sTST for the 1st 7 nights, Months 1, 2, 3, 4 and 5; and mean sTST at Month 6; for LEM5 and LEM10 compared to PBO
- Change from Study Baseline/ Treatment Period 2 Baseline of mean sSOL, mean sSE, mean sWASO and mean sTST for 1, 3, 6, 9 and 12 months exposure to LEM5 and LEM10. . Data from subjects randomized to LEM5 or LEM10 at the start of the study will use Study Baseline, data from subjects who were re-randomized to LEM5 or LEM10 in Period 2 will use Treatment Period 2 Baseline.
- The proportion of responders, separately for sSOL and sWASO, will be analyzed, for the first 7 nights, Months 1, 2, 3, 4, 5 and 6 for LEM5 and LEM10 compared to PBO:
 - The sleep onset responder is defined as: sSOL at Study Baseline is >30 minutes and mean sSOL at each month (first 7 nights, Months 1, 2, 3, 4, 5, 6) is ≤ 20 minutes,
 - The sleep maintenance responder is defined as: sWASO at Study Baseline is >60 minutes and mean sWASO at each month (first 7 nights, Months 1, 2, 3, 4, 5, 6) is ≤ 60 minutes and shows a reduction of >10 minutes compared to Study Baseline.

The proportion of responders will be analyzed based on the subjects with sSOL > 30 minutes at the baseline for sSOL and separately the subjects with sWASO > 60 minutes at the baseline for sWASO.

- The proportion of responders, separately for sSOL and sWASO, at Months 7, 8, 9, 10, 11 and 12 will also be summarized by using two types of baseline (ie., Study Baseline, Period 2 Baseline). The definition of the responder at Month 7, 8, 9, 10, 11 and 12 will be as follows:

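### The responder tests for sSOL and sWASO leave out the baseline value that sets how far each subject must fall; the tests are valid, but some precision is lost.

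*Protocol*

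**What the plan says.** Protocol 9.7.1.6.2 states: "The proportion of responders, separately for sSOL and sWASO, will be analyzed using the Cochran-Mantel-Haenszel test, adjusted for country and age group". SAP 3.4.2.4 states that "the portion of responders will be analyzed using the Cochran Mantel Haenszel (CMH) test adjusted for region and age group". The geographic factor differs, and baseline sSOL or sWASO is in neither test.

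Baseline enters elsewhere:

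- **Definition.** A sleep onset responder must reach a mean sSOL of 20 minutes or less. A sleep maintenance responder must reach a mean sWASO of 60 minutes or less in a record that "shows a reduction of >10 minutes compared to Study Baseline".
- **Denominator.** SAP 3.4.2.4 states: "The proportion of responders will be analyzed based on the subjects with sSOL > 30 minutes at the baseline for sSOL and separately", with a 60-minute cut for sWASO.
- **Continuous analyses.** The MMRMs of sSOL, sSE and sWASO (SAP 3.4.1 and 3.4.2.1) adjust for the corresponding baseline.
- **General statement.** SAP 3.3.2 says: "Baseline assessment, region, and age groups are used as covariates in the primary and secondary analyses".

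On missing data, SAP 3.4.2.4 says: "Missing values will be considered as non-responders in all responder analyses". Randomisation is stratified by country and age group (protocol 9.4.3). No multiplicity control is planned for these endpoints (protocol 9.7.1.6.2, SAP 3.3.3).

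**The concern.** With a fixed target, the starting point decides how hard it is to respond. For sSOL, a subject entering at 32 minutes needs a fall of 32 − 20 = 12 minutes; one entering at 100 needs 100 − 20 = 80. Baseline should therefore predict response, to an extent that depends on how strongly baseline and Month 6 values correlate. It is already collected, and restricting the denominator by baseline means that no analysed subject lacks it, so adjusting for it excludes nobody.

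Responder proportions are a named secondary objective. Leaving out a prognostic baseline makes the estimated difference from PBO less precise than it could be. This may matter more under the SAP denominator, which can be smaller than 300 per arm because entry requires sSOL and/or sWASO symptoms.

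**Working it through.** **1. The plan's own power figure.** Protocol 9.7.2 claims more than 99% power with 900 subjects (300 per arm) for differences of 16 points (sleep onset) and 24.4 points (sleep maintenance). It gives no placebo rate p0, so p0 is varied.

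Power = Φ[(d − 1.96·se0)/se1], where se0 = √(p̄(1−p̄)·2/n), se1 = √((p0(1−p0) + p1(1−p1))/n), p1 = p0 + d and p̄ is the mean of p0 and p1.

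For d = 0.16, p0 = 0.30 and n = 300: se0 = √(0.38×0.62×2/300) = 0.0396; se1 = √((0.21 + 0.2484)/300) = 0.0391; power = Φ(2.11) = 98.2%.

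At p0 = 10%, 20% and 42%, power is 99.9%, 99.3% and 97.6% (the last is the minimum). It strictly exceeds 99% only for p0 up to about 22.6%, but falls short by no more than 1.4 points. For d = 0.244 it is above 99.99% at every p0. The stated figure is essentially reproduced.

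**2. What baseline could add.** If baseline explains a share R² of within-arm responder variance, adjustment acts like raising n to n/(1 − R²). The documents give neither R² nor a correlation, so R² was simulated. Diary values were log-normal, only subjects above the baseline cut were analysed, and the baseline to Month 6 correlation was 0.2 to 0.7. Power came from 600 trials per row with 200 analysed per arm. It compares CMH over six region-by-age strata (unrelated to outcome) with logistic regression on treatment and log baseline. The true difference was about 13 to 14 points.

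| Endpoint | Correlation | Responders, PBO / active | R² | Effective n gain | Power, CMH | Power, logistic | Change (points) |
|---|---|---|---|---|---|---|---|
| sSOL | 0.2 | 27.7% / 41.3% | 0.014 | 1.4% | 86.0% | 85.2% | −0.8 |
| sSOL | 0.3 | 26.3% / 40.1% | 0.030 | 3.1% | 82.5% | 82.8% | +0.3 |
| sSOL | 0.5 | 23.1% / 37.2% | 0.083 | 9.0% | 84.2% | 86.3% | +2.1 |
| sSOL | 0.7 | 19.8% / 33.9% | 0.177 | 21.5% | 90.2% | 94.8% | +4.6 |
| sWASO | 0.2 | 24.2% / 37.2% | 0.016 | 1.6% | 79.8% | 80.8% | +1.0 |
| sWASO | 0.3 | 23.8% / 36.7% | 0.036 | 3.7% | 79.0% | 81.3% | +2.3 |
| sWASO | 0.5 | 22.5% / 35.6% | 0.104 | 11.6% | 82.3% | 85.0% | +2.7 |
| sWASO | 0.7 | 21.3% / 34.8% | 0.230 | 29.8% | 87.7% | 93.2% | +5.5 |

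Each power figure carries a Monte Carlo error of about 1.5 points, so the changes at 0.2 to 0.3 are hard to tell from zero. The variance of the standardised risk difference relative to the simple difference agrees: 0.97 to 1.02 at correlations of 0.2 to 0.3, 0.92 at 0.5, and 0.86 (sSOL) and 0.79 (sWASO) at 0.7.

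**3. At the planned 16-point sSOL difference.** Put n/(1 − R²) into the formula of step 1 with p0 = 30%:

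| Per arm | R² = 0 | 0.03 | 0.10 | 0.20 |
|---|---|---|---|---|
| 300 | 98.2% | 98.5% | 99.0% | 99.5% |
| 180 (assumed: 60% pass the cut) | 88.2% | 89.1% | 91.2% | 94.0% |

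For sWASO at 24.4 points and p0 = 30%, power exceeds 99.7% in every cell.

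**4. Baseline tertiles as extra CMH strata.** For sSOL at correlations of 0.2 and 0.3, this gave power of 85.2% and 81.2%, against 86.0% and 82.5% for plain CMH. For sWASO it gave 79.5% and 78.3%, against 79.8% and 79.0%. There is no gain at low correlation.

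**The case against.** The case for leaving the plan alone is substantial. CMH stratified by the randomisation factors, or by region as a pooling of country, is a standard and valid test. The same diary variables are analysed continuously with baseline as a covariate, so the responder test is a companion summary. Its planned power is already high, the gain is small unless the correlation is strong, and no gated conclusion depends on it. All of that stands. Dropouts scored as non-responders, whose outcome need not track baseline, could dilute the gain further; the simulation does not include them.

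One part does not stand: that the SAP already deals with baseline by restricting the denominator. The cut removes only the lower end. The entry criteria set no upper limit on sSOL or sWASO, so the variation above the cut remains and is unused.

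Two stronger readings are tempting. A reader might infer that chance baseline imbalance biases the responder comparison. It does not: under randomisation such imbalance is ordinary sampling variation, covered by the test's type 1 error. A reader might also infer from SAP 3.3.2 that the SAP contradicts itself. That sentence is general, and the specific rule in 3.4.2.4 can be read as governing. SAP 3.3.3 likewise speaks of secondary endpoint comparisons and then lists only the key secondaries, whose models do adjust for baseline. The wording is worth aligning but does not prove an error.

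**Conclusion.** The point holds as a matter of efficiency only. The responder tests omit a baseline value that is already collected and bears directly on response. The size rests on assumed correlations, placebo rates and fractions passing the cut, none of which the documents give. The loss is small at correlations of 0.2 to 0.3, moderate at 0.5 and material only near 0.7.

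A reader might conclude that the responder analysis is underpowered. The documents do not support that: at the planned differences with 300 per arm, power is 97.6% or more for sSOL and above 99.99% for sWASO. Adjustment is most useful if the true sSOL difference is below 16 points or if the SAP denominator is well below 300 per arm. This is an inexpensive improvement worth prespecifying, not a flaw in validity.

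**What to change.** In SAP 3.4.2.4 and protocol 9.7.1.6.2 (and the matching synopsis text), make the Period 1 responder analysis a logistic regression with treatment, age group, one geographic factor and continuous baseline: log sSOL for sleep onset, sWASO for sleep maintenance. The simulation used log baseline for both, so the SAP should fix the sWASO scale in advance. Use the same geographic factor, country or region, in both documents.

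Report the standardised (marginal) risk difference versus PBO for each dose with its 95% CI, and state how the CI is obtained. Keep missing values as non-responders and keep CMH as a supportive analysis. Do not use baseline tertiles as CMH strata instead. Align SAP 3.3.2 with 3.4.2.4 so that it is clear which secondary analyses carry the baseline covariate.

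The cost is wording in both documents and one model statement, settled before Period 1 is unblinded. There is no new data collection and no effect on the gatekeeping sequence.
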